3.3.2 Secondary Endpoints

Secondary efficacy endpoints assess the effect of IV Ampion compared to SOC on the clinical outcomes for participants with COVID-19 who require supplemental oxygen as follows:

Objective	Endpoint
Secondary Endpoints	
Assess the effect of Ampion compared to placebo on safety	
Incidence of adverse events (AEs) and serious adverse events (SAEs) from baseline to Day 60.
Assess the effect of Ampion compared to placebo on hospital stay	
Hospital length of stay (LOS) from admission to discharge.
Assess the effect of Ampion compared to placebo on oxygen use	
Duration of oxygen use, blood oxygen saturation, and oxygen flow rate from baseline through Day 5.
Assess the effect of Ampion compared to placebo on duration of respiratory failure to ventilator-free days	
Percentage of participants who progress to respiratory failure (i.e., need for mechanical ventilation, ECMO, non-invasive ventilation) by Day 28.
Assess the effect of Ampion compared to placebo on intensive care	
Percentage of participants who require Intensive Care Unit (ICU) admission by Day 28.ICU-free days through Day 28.ICU LOS from ICU admission to discharge.
Assess the effect of Ampion compared to placebo on clinical improvement	
Change in ordinal scale from baseline through Day 7.Change in ordinal scale from baseline to hospital discharge or Day 14 (whichever occurs first).

Objective	Endpoint
	
Change in ordinal scale from baseline to hospital discharge or Day 28 (whichever occurs first).
Assess the effect of Ampion compared to placebo on clinical health	
Change in NEWS2 score from baseline through Day 5.Change in NEWS2 score from baseline to hospital discharge.
Assess the effect of Ampion compared to placebo on oxygen use	
Duration of oxygen use, blood oxygen saturation, and oxygen flow rate from baseline through Day 5.

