4.4 Inclusion Criteria

Patients should fulfill all the following inclusion criteria:

1. Male or female, ≥ 18 years old.
2. Diagnosed with COVID-19, as evaluated by laboratory diagnostic test or diagnosis based on radiological clinical findings.
3. Baseline severity categorization of severe or critical COVID-19 infection per FDA Guidance for developing drugs and biological products for COVID-19 (February 2021):
 - a) Severe COVID-19:
 - Symptoms suggestive of severe systemic illness with COVID-19, which could include shortness of breath or respiratory distress
 - Clinical signs indicative of severe systemic illness with COVID-19, such as respiratory rate ≥ 30 per minute, heart rate ≥ 125 per minute, $\text{SpO}_2 \leq 93\%$ on room air at sea level ($\text{SpO}_2 \leq 90\%$ at altitude) or $\text{PaO}_2/\text{FiO}_2 \leq 300$
 - b) Critical COVID-19:
 - Oxygen delivered by high-flow nasal cannula (heated, humidified, oxygen delivered via reinforced cannula at flow rates > 20 L/min with fraction of oxygen ≥ 0.5) or
 - Non-invasive mechanical or endotracheal mechanical ventilation
4. Informed consent obtained from the patient or the patient's legal representative.

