5.2 Assessment Methods

Demographic Data

Demographic data will be collected from medical records: age, gender, race, height and weight, comorbidities.

Medical History

Medical history and pre-existing conditions will be collected from medical records.

Concomitant Medications

Concomitant medications will be collected from the medical records: prior (pre-hospitalization) concomitant medications, in-patient concomitant medications.

Mortality

All-cause mortality will be recorded at hospital discharge, Days 28 and 60, as applicable. Cause of mortality will be assessed and documented. All-cause mortality is calculated for the primary endpoint as the percentage of participants with a successful outcome (life) or unsuccessful outcome (death).

Length of Stay (LOS)

Due to the COVID-19 health emergency, the Centers for Medicare and Medicaid is temporarily allowing long-term care facilities not normally used as a resident's room to accommodate beds and residents for care in emergencies/situations needed to help with surge capacity. Therefore, hospitalization refers to hospital and/or inpatient care during the COVID-19 health emergency. Inpatient care may include hospitals treating COVID-19 patients; dedicated COVID-19 treatment facilities with 24/7 care; and/or dedicated research facilities with 24/7 care.

Dates of hospitalization and ICU admission as well as discharge dates will be recorded at hospital discharge, Days 28 and 60, as applicable. The hospital LOS and ICU LOS will be calculated as follows:

- ICU admission: defined (in days) as the first study day when ICU status is changed to “yes” minus baseline date + 1
- Hospital LOS: is defined (in days) as the date of hospital discharge minus date of hospital admission + 1
- ICU LOS: defined (in days) as the date moved out of ICU minus first study date when ICU admission changed to “yes” + 1

Oxygen Use

Oxygen use measured as blood oxygen saturation (SpO2) and oxygen flow rate (liters per minute, lpm) will be recorded at every visit from baseline to Day 5.

Intubation/Extubation

Date and time of intubation/extubation and days on ventilator will be recorded at hospital discharge, Days 28 and 60, as applicable. Proportion of participants who progress to respiratory failure (i.e., need for mechanical ventilation, ECMO, non-invasive ventilation, or high-flow nasal cannula oxygen) will be evaluated.

Vital Signs

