9.4.2 Secondary Endpoints

Secondary efficacy endpoints assess the effect of IV Ampion compared to SOC on the clinical outcomes for participants with COVID-19 on supplemental oxygen. The secondary endpoints will be tested in a hierarchical manner in the order presented, and thus no adjustment to the alpha level is necessary:

Objective	Endpoint
Secondary Endpoints	
Assess the effect of Ampion compared to placebo on safety	
Incidence of adverse events (AEs) and serious adverse events (SAEs) from baseline to Day 60.
Assess the effect of Ampion compared to placebo on clinical improvement	
Change in ordinal scale from baseline through Day 7.Change in ordinal scale from baseline to hospital discharge or day 14 (whichever occurs first).Change in ordinal scale from baseline to hospital discharge or day 28 (whichever occurs first).Change in NEWS2 score from baseline through Day 5.Change in NEWS2 score from baseline to hospital discharge.Modulation of cytokine levels from baseline to Day 5.
Assess the effect of Ampion compared to placebo on duration of respiratory failure to ventilator-free days.	
Percentage of participants who progress to respiratory failure (i.e., need for mechanical ventilation, ECMO, non-invasive ventilation) by Day 28.

Objective	Endpoint
Assess the effect of Ampion compared to placebo on intensive care	
Percentage of participants who require Intensive Care Unit (ICU) admission by Day 28.ICU-free days through Day 28.ICU LOS from ICU admission to discharge.
Assess the effect of Ampion compared to placebo on hospital stay	
Hospital length of stay (LOS) from admission to discharge.Hospital-free days through Day 28.
Assess the effect of Ampion compared to placebo on oxygen use	
Duration of oxygen use, blood oxygen saturation, and oxygen flow rate from baseline through Day 5.

The efficacy endpoints will be evaluated to estimate the treatment effect and use descriptive statistics including mean, standard deviation, percentages, minimum/maximum, and 95% confidence intervals. All endpoints will be tabulated and presented by treatment arm, cohort (severe and critical), and timepoint. Where appropriate, data will be tabulated and presented cumulatively across cohorts and/or timepoints.

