3.2 Secondary Endpoints

3.2.1 Change in ordinal scale from baseline through Day 7, Day 14 and Day 28.

The hypotheses to be tested are:

$$H_0: \mu_A = \mu_S \text{ versus } H_A: \mu_A \neq \mu_S$$

Where μ_A and μ_S represent the ordinal scale shift through day 7, 14, and 28 for Ampion and Placebo after randomization. The difference between Ampion and Placebo with respect to the change from baseline at day 7, 14, and 28 will be tested utilizing a Wilcoxon rank-sum test via PROC NPAR1WAY. To assess any potential time trends, an exploratory repeated measures analysis of variance will be performed with terms for treatment, time and the interaction between the two. This will be done utilizing PROC GLM with the REPEATED option.

3.2.2 Change in NEWS2 score from baseline through Day 7, or discharge if earlier.

The hypotheses to be tested are:

$$H_0: \mu_A = \mu_S \text{ versus } H_A: \mu_A \neq \mu_S$$

Where μ_A and μ_S represent the mean change from baseline in the NEWS2 score assessment through day 7 for Ampion and Placebo after randomization. The difference between Ampion and Placebo with respect to the change from baseline at day 7, or discharge if earlier, will be tested utilizing a Wilcoxon rank-sum test via PROC NPAR1WAY. To assess any potential time trends an exploratory repeated measures analysis of variance will be performed with terms for treatment, time and the interaction between the two. This will be done utilizing PROC GLM with the REPEATED option.

3.2.3 Percentage of participants who progress to respiratory failure by Day 28.

The hypotheses to be tested are:

$$H_0: \pi_A = \pi_S \text{ versus } H_A: \pi_A \neq \pi_S$$

Statistical Analysis Plan (SAP) for Clinical Study AP-017

Let π_A and π_S represent the percentage of patients who have respiratory failure for Ampion and control during the first 28 days after randomization.

This difference will be tested utilizing the appropriate chi-square test or Fisher's exact test utilizing PROC FREQ with the EXACT option, if needed.

Also, the median time to respiratory failure will be tested for difference between the two groups via the log-rank test. The log-rank test will be performed using PROC LIFETEST; and the estimation of the time-to-event distributions will be performed using the method of Kaplan and Meier.

3.2.4 Percentage of participants who require Intensive Care Unit (ICU) admission by Day 28; ICU-free days through Day 28; ICU length of stay (LOS) from ICU admission to discharge.

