There are two endpoints in this set. Hypotheses about both will be tested independently. The first hypothesis about the percentage of patients who are admitted to the ICU involves all patients. The second hypothesis involves only patients who are admitted to the ICU. Since it is not known how many many patients will be admitted to the ICU, the testing of the second hypothesis will be considered exploratory and not part of the hierachial testing scheme.

The first hypotheses to be tested is:

$$H_0: \pi_A = \pi_S \text{ versus } H_A: \pi_A \neq \pi_S$$

Where π_A and π_S represent the percentage of patients who are admitted to the ICU for Ampion and Placebo during the first 28 days after randomization. The difference between Ampion and Placebo will be tested via an appropriate chi-square test or Fisher's exact test utilizing PROC FREQ with the EXACT option, if needed.

The second hypothesis to be tested is:

$$H_0: \text{Median}_A = \text{Median}_S \text{ versus } H_A: \text{Median}_A \neq \text{Median}_S$$

Where Median_A and Median_S are the median ICU length of stay for the Ampion and placebo groups. Assuming there is no censoring, this will be tested using the Wilcoxon rank sum test via PROC NPAR1WAY. If censoring occurs, e.g., death, then the log rank test will be used based on PROC LIFETEST.

3.2.5 Modulation of cytokine levels from baseline to Day 5.

The hypotheses to be tested are:

$$H_0: \mu_A = \mu_S \text{ versus } H_A: \mu_A \neq \mu_S$$

Where μ_A and μ_S represent the mean percent change from baseline in the cytokine levels at day 5 for Ampion and Placebo after randomization. The difference between Ampion and Placebo with respect to the percent change from baseline at day 5 will be tested utilizing a two sample t-test via PROC TTEST. To assess any potential time trends an exploratory repeated measures analysis of variance will be performed with terms for treatment, time and the interaction of the two. This will be done utilizing PROC GLM with the REPEATED option.

Statistical Analysis Plan (SAP) for Clinical Study AP-017

3.2.6 Hospital length of stay.

The hypotheses to be tested are:

$$H_0: \text{Median}_A = \text{Median}_S \text{ versus } H_A: \text{Median}_A \neq \text{Median}_S$$

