10.3 Figures

Note that all figures, unless otherwise stated, will be line plots showing mean \pm SEM at each visit for each treatment arm.

1. Summary of mechanical ventilation and mortality [i.e. Bar Graph]
2. Summary of ordinal scale
3. Summary of NEWS2 score
4. Summary of progression to respiratory failure at day 28
5. Summary of ICU admission and ICU Length of stay (LOS)
6. Summary of cytokine levels
7. Summary of ventilator free days (i.e. Survival curve)
8. Summary of days on ventilation
9. Summary of hospital length of stay (i.e. Survival curve)

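### The objective on duration of respiratory failure and ventilator-free days is tested only as an incidence and a time to onset, with two definitions of respiratory failure and no rule for patients already in that state at entry

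*Protocol*

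**What the plan says.** **Objective and endpoint.** The protocol synopsis, 3.3.2 and 9.4.2 all carry the objective "Assess the effect of Ampion compared to placebo on duration of respiratory failure to ventilator-free days". The one endpoint set against it is "Percentage of participants who progress to respiratory failure (i.e., need for mechanical ventilation, ECMO, non-invasive ventilation) by Day 28".

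**Analysis.** SAP 3.2.3 compares proportions that "represent the percentage of patients who have respiratory failure for Ampion and control during the first 28 days after randomization", by chi-square or Fisher's exact test, and adds a log-rank test of time to respiratory failure. Protocol 9.4.2 names Fisher's exact test for binary outcomes. Ventilator-free days and days on ventilation appear in SAP Listing 15 and Figures 7 and 8. No section of the SAP defines them or gives a hypothesis, a rule for death or a test.

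**Definition.** Protocol 5.2 (Intubation/Extubation) gives a wider list: "need for mechanical ventilation, ECMO, non-invasive ventilation, or high-flow nasal cannula oxygen". The synopsis, 3.3.2 and 9.4.2 leave high-flow cannula out.

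**Entry.** Criterion 3b in Protocol 4.4 defines critical disease as high-flow nasal oxygen or "Non-invasive mechanical or endotracheal mechanical ventilation". Exclusion 2 in Protocol 4.5 bars a clinical diagnosis of respiratory failure, with an unclear qualifier about resource limitation.

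**Population and order.** Efficacy is analysed in all randomised patients (Protocol 9.2.2, SAP 5.1.2). Secondary endpoints are tested in a fixed order (Protocol 9.4.2, SAP 8.6). Respiratory failure is third in SAP 3.2, ahead of ICU admission, cytokines and hospital stay.

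**The concern.** There are three linked gaps.

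1. Neither an incidence by Day 28 nor a time to onset measures duration. A patient ventilated for 2 days and one ventilated for 25 days count the same in the only formal test.
2. The two definitions can give different event counts from the same data.
3. A patient who enters in the state cannot progress to it, yet stays in the denominator. If such patients are counted as having respiratory failure, they add similar numbers of events to both arms whatever the treatment, and their time to onset is zero. That shrinks the difference at a gating step: failure there stops formal testing of everything after it.

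**Working it through.** **Step 1. Who is already in the state at entry?**

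| Support at entry (criterion 3b) | 3.3.2 / 9.4.2 definition | 5.2 definition |
|---|---|---|
| Non-invasive or endotracheal ventilation | in respiratory failure | in respiratory failure |
| High-flow nasal cannula | not in respiratory failure | in respiratory failure |

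The documents do not give the share of patients in either row. Exclusion 2, depending on how it is read, could remove some of them.

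**Step 2. The plan's own power figure.** It is for the primary endpoint only: 8% v 22%, 100 per arm, two-sided 5%, unpooled z-test by binomial enumeration, stated as 81.3%. Enumerating all 101 × 101 outcomes gives 81.28%, so it reproduces. Fisher's exact test on the same inputs gives 75.8%. No rate or power is stated for respiratory failure.

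**Step 3. Effect of baseline cases.** All inputs except the sample size and alpha are assumptions. Let c be the share of each arm already in the state, and r the progression rate among the rest (30% placebo, 13% Ampion).

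- Counted as events: p = c + (1 − c)r, n = 100 per arm.
- Counted as non-events: p = (1 − c)r, n = 100 per arm.
- At-risk subset: p = r, n = 100(1 − c) per arm.

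At c = 0.30:

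- Events: 0.30 + 0.70 × 0.30 = 51.0% v 0.30 + 0.70 × 0.13 = 39.1%. The difference is 11.9 points instead of 17, and the risk ratio is 0.77 instead of 0.43.
- Non-events: 0.70 × 0.30 = 21.0% v 0.70 × 0.13 = 9.1%. The difference is again 11.9 points, but on a lower background rate.
- At risk: 30% v 13% with 70 per arm.

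Power, unpooled z by enumeration, two-sided 0.05:

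| c | as events | as non-events | at-risk subset |
|---|---|---|---|
| 0 | 85% | 85% | 85% |
| 0.15 | 60% | 77% | 79% |
| 0.30 | 41% | 67% | 71% |
| 0.40 | 32% | 59% | 64% |

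With Fisher's exact test the c = 0 figure is about 80%. At c = 0.30 it is about 36% as events and 63% in the at-risk subset.

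**Step 4. Sensitivity to the assumed rates.** Borrow 22% v 8% from the primary endpoint, with c = 0.30. The pooled z-test (equivalent to the uncorrected chi-square) gives 30% as events, 64% as non-events and 66% at risk. Fisher's test gives 25%, 55% and 58%.

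These figures let the number of baseline cases differ between arms by chance. Fixing it at exactly 30 per arm lowers the pooled-z figure as events from 30% to 18.5% and leaves the non-event figure at about 65%.

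**The case against.** **Every label speaks of progression.** The endpoint, the SAP 3.2.3 heading and the planned table and listing all use that word, and only the parameter sentence speaks of patients who *have* respiratory failure. A reader might infer that baseline cases are certain events and that power must fall to about 41%. The documents do not support that: counting them as non-events is equally open and costs little (67% against 71%). What stands is that no rule is written, and the choice between two permitted readings moves power by about 26 points in the illustration.

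**The critical stratum.** A reader might infer that the whole stratum is in respiratory failure at entry. Under 3.3.2 and 9.4.2 it is not, because high-flow patients are not yet in the state. It is true only under 5.2.

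**Exclusion 2.** If it is applied to keep ventilated patients out, dilution under the narrower definition could be near zero. But 3b expressly admits them, so exclusion 2 does not settle the matter.

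**Duration is reported.** Listing 15 and Figures 7 and 8 would show ventilator-free days and days on ventilation, and summaries by severity are planned (Protocol 9.3.1.5). So the objective is untested, not unreported. Descriptive displays do not replace a defined endpoint.

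**ICU admission.** SAP 3.2.4 says "The first hypothesis about the percentage of patients who are admitted to the ICU involves all patients", and a reader might see the same flaw there. Protocol 5.2 dates ICU admission from the study day on which status changes to yes. That describes a transition, so a patient in ICU at baseline is not clearly an event. A clarifying sentence is enough.

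**Conclusion.** The point holds in this form. The stated objective has no matching tested endpoint, respiratory failure has two conflicting definitions, and patients who may enter in that state are analysed without a rule. The first two follow directly from the text.

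The size of the third is unknown. It depends on the share in the state at entry, on which definition applies, on how exclusion 2 is read, and on how baseline cases are coded. At an assumed 30% share and 30% v 13% progression, power ranges from about 41% (events) to 67% (non-events), against 71% in the at-risk subset. The loss could be near zero if few such patients enrol. This is a secondary endpoint, so the primary test is untouched, but the endpoint gates later tests. It should be corrected before unblinding.

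**What to change.** (a) Add ventilator-free days through Day 28, with death given the worst value, as the endpoint for this objective. Test it by a rank test in the ITT population and state its place in the fixed order. Intubation and extubation dates and days on ventilation are already collected. Label it as ventilator-free days rather than duration of respiratory failure, because start and stop dates for non-invasive ventilation and high-flow oxygen are not listed for collection.

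(b) Use one definition of respiratory failure in the synopsis, Protocol 3.3.2, 5.2 and 9.4.2, and SAP 3.2.3.

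(c) Test progression, and time to it, only in patients not in that state at baseline. The subset is fixed before treatment, so the randomised comparison is kept. Baseline oxygen mode and the Day 0 ordinal score are already recorded and should identify it.

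(d) Reconcile exclusion 2 with criterion 3b.

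(e) State in SAP 3.2.4 that ICU admission means a change of status after baseline.

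The cost is protocol and SAP wording and one more table. The real downside is a smaller denominator in (c). Under the 5.2 definition it removes the critical patients already on such support from the progression test. They would still contribute to ventilator-free days.

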1.2 Schedule of Assessments (SoA)

Visits will be conducted as described:

	Screen	Treatment					Hospitalization/ Continued Care	Follow-Up		
Study Day	-3 to 0	0	1	2	3	4	5	Every day until Day 7	28	60
Visit Window (± days)	--	--	--	--	--	--	--	--	3	3
COVID-19 diagnosis	X									
Informed consent	X									
Medical history and pre-existing conditions	X									
Inclusion/exclusion criteria	X	X								
Urine pregnancy test ¹		X								
Demographics		X								
Randomization		X								
IV treatment			X	X	X	X	X			
Vital signs		X	X	X	X	X	X	X		
Blood oxygen saturation		X	X	X	X	X	X	X		
ECG monitoring (telemetry) ²		X	X	X	X	X	X	X ²		
Hematology ³		X		X		X	X	X ³		
Biochemistry ²		X		X		X	X	X ³		
Cytokine/chemokine assay ⁴		X				X		X ⁴		
Mortality								X	X	X
Ordinal scale for clinical status		X	X	X	X	X	X	X	X	X
NEWS2 score for clinical status		X	X	X	X	X	X	X	X	X
Hospital LOS and ICU LOS			X	X	X	X	X	X	X	X
Date of intubation/ extubation, days on ventilation			X	X	X	X	X	X	X	X
Concomitant medications		X	X	X	X	X	X	X	X	X
Adverse events		X	X	X	X	X	X	X	X	X

¹ As applicable

² Telemetry monitored as needed for patients who have events or abnormal readings requiring measurements.

³ Hematology and biochemistry tests are performed at baseline and every other day through treatment and inpatient stay unless an abnormal value is observed. In the case of an abnormal lab result, continue to collect and test those samples to follow subject through resolution.

⁴ Cytokine and chemokine assays are collected at baseline before treatment, at Day 5 after treatment, and at discharge.

TABLE OF CONTENTS

1	PROTOCOL SUMMARY	3
1.1	Protocol Synopsis.....	3
1.2	Schedule of Assessments (SoA)	9
2	INTRODUCTION	14
2.1	Study Drug	14
2.2	Background to the Disease.....	14
2.3	Previous Human Experience.....	15
2.4	Study Rationale.....	16
2.4.1	Study Background.....	16
2.4.2	Preclinical Data.....	16
2.4.3	Dosing Rationale.....	17
2.5	Benefit and Risk Assessment.....	18
3	STUDY DESIGN.....	19
3.1	Study Design Overview	19
3.2	Study Objectives	20
3.2.1	Primary Objective	20
3.2.2	Secondary Objectives.....	20
3.3	Study Endpoints.....	20
3.3.1	Primary Endpoint	20
3.3.2	Secondary Endpoints	20
3.4	Blinding and Randomization	21
3.5	Data Safety Monitoring Board.....	21
3.6	Stopping rules	21
4	SELECTION OF PARTICIPANTS	22
4.1	Number of Participants	22
4.2	Recruitment Methods.....	22
4.3	Participant Characteristics	22
4.4	Inclusion Criteria	23
4.5	Exclusion Criteria	23

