5.1.4 Hospitalization Period, as applicable (Day 6 through Day 7)

Hospitalization refers to hospital and/or in-patient settings. The following procedures will be performed for the remainder of the hospitalization, as applicable:

- Concomitant medications/therapies
- Vital signs: heart rate, systolic and diastolic BP, body temperature, respiratory rate
- SpO2 and supplementation oxygen mode/flow rate
- ECG monitoring (telemetry) or 12-lead ECG: record aberrant changes in waves/ intervals – monitored as needed for patients who have abnormal readings or events requiring measurements.
- Hematology, biochemistry tests – these tests are performed at baseline and every other day through treatment and through hospital stay unless an abnormal value is observed. In the case of an abnormal lab result, continue to collect and test those samples to follow subject through resolution.
- Cytokine and chemokine assays – these tests are performed at hospital discharge.
- Ordinal scale and NEWS2 assessments
- AEs

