5.1.5 Post-Treatment Follow-Up (Days 28, 60)

The following procedures will be performed at all follow-up visits (Days 28, 60):

- Mortality
- Concomitant medications/therapies
- Hospital LOS
- ICU LOS
- Ordinal scale and NEWS2 assessments
- AEs

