8.6 Multiplicity Adjustment

The secondary analyses are considered supportive to the primary analysis. In order ensure the appropriate alpha level for all tests (without a multiplicity adjustment) a hierachial testing scheme will be employed in the order specified in Section 3.2.

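### The Day 14 ordinal-scale endpoint is part of the testing hierarchy, but the protocol and SAP schedules contradict each other on whether it is collected

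*Protocol*

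**What the plan says.** **Endpoint.** Protocol 3.3.2 defines it as "Change in ordinal scale from baseline to hospital discharge or Day 14 (whichever occurs first"; a parallel endpoint runs to discharge or Day 28. SAP 3.2.1 has no discharge cut-off: the "change from baseline at day 7, 14, and 28 will be tested utilizing a Wilcoxon rank-sum test via PROC NPAR1WAY".

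**Testing order.** Protocol 9.4.2 states: "The secondary endpoints will be tested in a hierarchical manner in the order presented, and thus no adjustment to the alpha level is necessary". There the Day 14 change stands third, after adverse events and the Day 7 ordinal change. It precedes the Day 28 change, NEWS2, cytokines, respiratory failure, ICU outcomes, hospital stay and oxygen use. SAP 8.6 says a "hierachial testing scheme will be employed in the order specified in Section 3.2", and Days 7, 14 and 28 together form the first item of that section.

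**Protocol schedule.** In Protocol 1.2 the row "Ordinal scale for clinical status" is marked at Days 0 to 5, in the column "Every day until Day 7", and at Days 28 and 60. Section 5.1.5 agrees: "The following procedures will be performed at all follow-up visits (Days 28, 60". Section 5.2 ties the score to visits, so where there is no visit no score is due.

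**Inpatient period.** The heading of Protocol 5.1.4 is "Hospitalization Period, as applicable (Day 6 through Day 7". The text below it has the listed procedures, the ordinal scale among them, continue until the hospital stay ends. The table of contents also runs that section to discharge.

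**SAP schedule.** SAP Section 12 adds follow-up columns for Days 7 and 14 and marks the ordinal scale in both.

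**The concern.** The statisticians expect a Day 14 score that the protocol schedule does not ask sites to obtain. Under Protocol 10.3, additions to the protocol require a written, approved amendment, so a column in the SAP does not create a site contact. SAP Section 9, which lists changes from the protocol's analyses, mentions neither the added visit nor the changed endpoint definition.

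What is at stake is a formally tested endpoint with scores missing for a reason tied to outcome. Under the protocol's definition, the patients without a scheduled score are the survivors who stay beyond Day 7. If treatment affects length of stay, the arms will differ in who is missing, and an analysis of available scores would compare selected early discharges and deaths. The missing-data provisions (Protocol 9.5; SAP 7.1) cover adverse events, medication dates, mortality and the primary endpoint, but not the ordinal scale. Neither document says how the testing sequence proceeds if a step lacks data, so whatever is done would be decided after the fact.

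**Working it through.** The plan states no figure for this endpoint. Its one power figure, about 81.3% for the primary endpoint, reproduces (81.28% by exact enumeration) and does not enter here. The check is of which days and patients are covered.

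**1. Days covered by the protocol schedule**

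- Scores due (Protocol 1.2): Days 0 to 7, then Day 28 ± 3 and Day 60 ± 3.
- Earliest Day 28 visit: 28 − 3 = Day 25.
- Uncovered interval: Days 8 to 24, which is 24 − 8 + 1 = 17 days.
- Distance from Day 14 to the last scheduled score: 14 − 7 = 7 days before.
- Distance from Day 14 to the next possible score: 25 − 14 = 11 days after.

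No visit window brings a scheduled score to Day 14.

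**2. Who has a score, by definition and by reading of the protocol**

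| Survivors | Discharge or Day 14 (protocol); schedule in 1.2 | Discharge or Day 14; 5.1.4 text read to discharge | At Day 14 (SAP); schedule in 1.2 | At Day 14; 5.1.4 text read to discharge |
|---|---|---|---|---|
| Discharged by Day 7 | Yes | Yes | No | No |
| Discharged Days 8–13 | No | Yes | No | No |
| In hospital on Day 14 | No | Yes | No | Yes |

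Deaths can be scored 8 in every column. The SAP Section 12 schedule would fill the SAP's definition for all three groups. It has no explicit ordinal score at discharge, so even there the protocol's definition is not clearly served for discharges on Days 8 to 13.

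**3. Whether other recorded data can fill the gap**

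Protocol 5.2 records dates of hospital and ICU admission and discharge, intubation and extubation, and mortality. On the WHO scale these separate death, ventilated inpatients, unventilated inpatients and discharged patients. They do not separate scores 0 to 2 after discharge, 3 to 5 in unventilated inpatients, or 6 from 7. Scheduled oxygen saturation ends at Day 7 (Protocol 1.2), and oxygen flow is recorded to Day 5 (Protocol 5.2). Recovery is therefore partial.

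**4. The Day 28 endpoint**

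Under discharge or Day 28, whichever is first, a patient discharged on Days 8 to 24 falls in the same 17-day interval and has no clearly scheduled discharge score. The defect is therefore not confined to Day 14.

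**The case against.** The best defence is that the protocol does provide for these scores. The text of 5.1.4 and its contents entry carry inpatient scoring to discharge. Footnotes to the Protocol 1.2 table carry laboratory and cytokine sampling into the inpatient stay or to discharge. Section 3.1 has evaluations from Day 7 to Day 60 done by telephone unless the patient is an inpatient. On that reading the protocol's own endpoint is computable for everyone, and the SAP schedule supplies Day 14 explicitly. The secondaries are also described in SAP 8.6 as supportive.

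Much of this stands. A reader might infer from the schedule alone that the endpoint cannot be computed, or has no data. The documents do not support that. Under the protocol's definition, deaths and patients discharged by Day 7 have a value, 5.1.4 can be read to cover the rest, and recorded dates give a coarse status. A reader might also infer that the gap blocks every later test. That is one possible consequence, but neither document says so, and the SAP groups Days 7, 14 and 28 as a single item without saying how each day gates what follows.

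The objection does not remove the contradiction. The 5.1.4 heading and the schedule table stop at Day 7, and a site may reasonably follow them. Even the generous reading leaves the SAP's definition without a scheduled Day 14 score for patients already discharged.

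**Conclusion.** The point holds as an inconsistency between the documents, and within the protocol, that affects a tested endpoint.

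- The protocol and SAP schedules disagree on Day 14, and Protocol 5.1.4 disagrees with itself on whether inpatient scoring ends at Day 7 or at discharge.
- If sites follow the protocol schedule, survivors in hospital after Day 7 lack a scheduled score under the protocol's definition, and all survivors lack one under the SAP's.
- The share of patients affected cannot be computed, because neither document gives an expected length of stay.

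The conclusion assumes that sites work from the protocol's schedule table and section headings, which is likely but not stated. No sample-size or power figure changes. The matter should be settled while data are being collected, since finer ordinal scores not recorded then may not be recoverable.

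**What to change.** 1. Amend Protocol 1.2, 5.1.4 and 5.1.5 to add a Day 14 ordinal assessment, by chart review for inpatients and by telephone for discharged patients, matching SAP Section 12.
2. Add an ordinal score at hospital discharge, whenever it occurs, to the same protocol sections, and show it in SAP Section 12 as well.
3. Reconcile the 5.1.4 heading with its text, the contents entry and the schedule table.
4. Use one definition in both documents: either the earlier of discharge and Day 14 (or 28), or the fixed day. Record the change in SAP Section 9.
5. State in the SAP how missing ordinal scores are handled, and how the testing order proceeds if a step lacks data.

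The cost is a protocol amendment, with the approvals that Protocol 10.3 requires, and one short contact per patient that the SAP already assumes. Deleting Day 14 from both documents would also need an amendment and would not be enough, because the endpoint to discharge or Day 28 would still lack a clearly scheduled score for discharges on Days 8 to 24.
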